## **2 INTRODUCTION**

### **2.1 STUDY RATIONALE**

Coronavirus Disease-19 (COVID-19) is caused by the severe acute respiratory syndrome coronavirus-2 (SARS-CoV-2) and is associated with significant mortality. Currently, two therapies have shown efficacy in large multicenter trials for the treatment of COVID-19, one of which is an antiviral (remdesivir) and the other is an immunosuppressant corticosteroid meant to dampen the immune response (dexamethasone). This study is designed to evaluate the safety and early efficacy of fostamatinib in addition to standard of care for hospitalized patients with COVID-19.

### **2.2 BACKGROUND**

COVID-19 first described in Wuhan, China in December of 2019 and subsequently has resulted in a global pandemic with an excess of 3 million infections and over 130,000 deaths as of early July 2020 in the United States. SARS-CoV-2 primarily infects the upper and lower respiratory tract and can lead to acute respiratory distress syndrome (ARDS) in a subset of patients with a known high mortality rate. Additionally, some patients develop other organ dysfunction including myocardial injury, acute kidney injury, shock along with endothelial dysfunction and subsequently micro and macrovascular thrombosis (Berlin, Gulick & Martinez, 2020). Much of the underlying pathology of SARS-CoV-2 is thought to be secondary to a dysregulated immune response and more recently a hypercoagulable state leading to immunothrombosis (Rapkiewicz et al., 2020).

Currently, two therapies have shown efficacy in large multicenter trials for the treatment of COVID-19, one of which is an antiviral (remdesivir) (Beigel, 2020) and the other is an immunosuppressant corticosteroid meant to dampen the immune response (dexamethasone) ("Dexamethasone in Hospitalized Patients with Covid-19 — Preliminary Report", 2020). Meanwhile many other immunomodulators are under investigation that may provide a much more targeted mechanism of action than broad acting steroids, which in some patients may actually worsen outcomes.

Spleen tyrosine kinase (SYK) is a cytoplasmic tyrosine kinase involved in the intracellular signaling pathways of many different immune cells. In this pilot study we propose to use fostamatinib (a SYK inhibitor) as a targeted therapy for the immunological complications of hospitalized patients with COVID-19. The biological mechanisms by which SYK inhibition may improve outcomes in patients with COVID-19 include the inhibition of pro-inflammatory cytokines by monocytes and macrophages, decreased production of neutrophil extracellular traps (NETs) by neutrophils, and inhibition of platelet aggregation; three pathways that are mediated through Fc receptors (FcR) recognition of antigen-antibody complexes or activation of c-type lectin receptors (CLEC) (Hoepel et al., 2020).

It is noted that a primary driver of SYK signaling is through the Fc $\gamma$ RIIA which is driven by immune antigen-antibody complex. It is becoming increasingly clear that there is an exuberant antibody response in patients with severe disease compared to those with less severe disease, a response that may be driven by viral load. By blocking this immune response, it is possible that fostamatinib may improve outcomes of patients with COVID-19. More specifically, in

monocytes and macrophages SYK is known to mediate the pro-inflammatory process through the production of pro-inflammatory cytokines such as IL-6. The production of pro-inflammatory cytokines has been reversed with the inhibition of SYK in MERS-CoV infected macrophages (Zhao et al., 2019). A recent study also found that anti-Spike IgG from serum of severely ill COVID-19 patients induces a hyperinflammatory response by human macrophages including elevated levels of IL-1 $\beta$ , IL-6, IL-8, TNF, and IL-10, a response that can be counteracted by SYK inhibition with fostamatinib. Furthermore, this study found that anti-Spike IgG is able to break down pulmonary endothelial barriers and induce microvascular thrombosis as evidenced by increase platelet adhesion and expression of von Willebrand's factor (Zhao et al., 2019).

In addition to the inhibition of the hyperinflammatory response from stimulated macrophages SYK inhibition of neutrophils and platelets may lead to decreased immunothrombosis resulting in less organ dysfunction in many patients with COVID-19 who become critically ill. In neutrophils SYK inhibition can lead to decreased production of neutrophil extracellular traps (NETs) which are known to be a driver of microthrombosis in heparin-induced thrombocytopenia, a process that is provoked by antigen-antibody complex stimulation of the Fc receptor (Zhao et al., 2019). In platelets SYK is known to inhibit multiple pathways associated with platelet aggregation including Fc $\gamma$ RIIA activation by immune complex, GPVI activation by collagen, and CLEC-2 activation by rhodocytin, all while not affecting ADP mediated platelet aggregation. By decreasing NET production and inhibiting platelet aggregation, SYK inhibition may lead to decreased immunothrombosis potentially decreasing organ dysfunction in patients with COVID-19 and ultimately improving outcomes.

Lastly, fostamatinib was identified in a screen of 3,373 compounds in different stages of development to reduce mucin-1 (MUC1) expression, a membrane bound molecule expressed on the apical surfaces of epithelial cells and a marker associated with increased severity of ARDS. In this study fostamatinib reduced MUC1 expression in lung epithelial cells in a mouse model of acute lung injury, providing additional rationale for why it may be advantageous in patients with COVID-19 ARDS (Alimova et al. 2020).

Fostamatinib is FDA approved in the US for the treatment of thrombocytopenia in adult patients with chronic immune thrombocytopenia (ITP) who have had insufficient response to a previous treatment and additionally, there is extensive experience with this drug in patients with rheumatoid arthritis (Weinblatt et al., 2008). Previous clinical reports support the clinical use of fostamatinib by showing it decreases interleukin-6 level in rheumatoid arthritis patient. Also, animal models using lipopolysaccharide induced inflammation have demonstrated that fostamatinib decreases acute lung injury and acute kidney injury (Al-Harbi et al., 2019) (Nadeem et al., 2019), making fostamatinib a candidate for the treatment of COVID-19. To date fostamatinib has not been used for the treatment of COVID-19. In light of overlapping toxicity between fostamatinib and other treatment modalities along with the clinical presentation of COVID-19 that can have significant overlap with the toxicities of fostamatinib we seek to perform a double blinded placebo control randomized clinical trial to test primarily safety of this drug in this hospitalized population.

## 2.3 RISK/BENEFIT ASSESSMENT

### 2.3.1 Known Potential Risks

#### Potential Risks of Fostamatinib:

Fostamatinib is FDA approved for the treatment of thrombocytopenia in adult patients with chronic immune thrombocytopenia (ITP) who have had an insufficient response to a previous treatment (FDA label 2020). To date, over 4,800 patients have received fostamatinib as part of randomized controlled and open label trials across a variety of disease states including rheumatoid arthritis, ITP, autoimmune hemolytic anemia, and oncologic diseases. It has a consistent safety profile and the most common adverse reactions ( $\geq 5\%$  and more than placebo) are diarrhea, hypertension, nausea, respiratory infection, dizziness, ALT/AST increased, rash, abdominal pain, fatigue, chest pain and neutropenia. Warnings and precautions included in the US product label include hypertension, elevated liver function tests, diarrhea, neutropenia, and embryo-fetal toxicity.

Hypertension	Hypertensive crisis occurred in 1% of patients and patients with pre-existing hypertension may be more susceptible
Hepatotoxicity	AST/ALT levels more than 3x the upper limited of normal occurs in 9% of patients
Diarrhea	Occurred in 31% of patients treated with severe diarrhea occurring in 1%
Neutropenia	Occurred in 6% of patients with febrile neutropenia occurring in 1%
Embryo-fetal toxicity	Based on findings from animal studies and mechanism of action fostamatinib can cause fetal harm.

Concomitant use with strong CYP3A4 inhibitors with fostamatinib will increase exposure to R406 that may result in increased risk of adverse reactions while concomitant use of strong CYP3A4 inducers reduces exposure to R406. Fostamatinib may increase the concentration of some CYP3A4 substrate drugs, some BCRP substrate drugs (ex. rosuvastatin), and some P-glycoprotein substrate drugs (eg. Digoxin).

It is not expected that there will be additive or synergistic adverse events with the addition of fostamatinib with standard of care except for remdesivir, which can cause increase in AST/ALT.

In addition to the fostamatinib adverse reactions listed above, the major potential risks of this study relate to the underlying disease (COVID-19) which has a high associated mortality in hospitalized patients. All subjects will be asked to provide personal identifiable information (PII). While every effort will be made to keep PII confidential, there is a chance PII may be obtained by unauthorized personnel. Electronic files will be password protected and all files will be locked in a cabinet or maintained in a locked room at the participating clinical site. Any publication will not have identifying information.

### 2.3.2 Known Potential Benefits

Fostamatinib may or may not improve the clinical outcome of individuals with COVID-19. However, there is benefit to society for their participation and insights may be gained about the therapeutic intervention under study. Additionally, individuals may benefit from a shortened disease course if fostamatinib is successful in this clinical trial.

### 2.3.3 Assessment of Potential Risks and Benefits

Fostamatinib has a consistent safety profile and adverse events are clearly documented. Currently the only immunomodulating therapy that has proven benefit in patients with COVID-19 is dexamethasone which improved mortality from 24.6% to 21.6% (RR 0.80, 95% CI 0.74-0.92,  $p < 0.001$ ) when compared to usual care in patients with COVID-19. This improvement in mortality was more dramatic in patients who required mechanical ventilation where mortality improved from 40.7% to 29.0%, resulting in a need to treat 8 patients to show benefit in one. However, the high mortality rate in the control group compared to usual care in the United States, the multiple randomizations permitted, and lack of remdesivir as part of usual care make interpreting the results of this study for patients in the United States difficult. Furthermore, the mechanism of action by which dexamethasone would improve outcomes is not known as steroids have indiscriminate broad ranging effects on immunosuppression. Fostamatinib has many potential advantages over steroids including a targeted mechanism of action that inhibits multiple pathways in the pathogenesis of COVID-19 including decreasing Fc receptor signaling on neutrophils, monocytes and macrophages and CLEC receptors on neutrophils and platelets. Through these mechanisms we hypothesize that fostamatinib will decrease the immunodysregulation associated with COVID-19 along with the NETosis and inflammatory driven immunothrombosis that precedes much of the organ failure.

## 3 OBJECTIVES AND ENDPOINTS

The primary objective of this study is to evaluate the safety of fostamatinib for the treatment of hospitalized patients with COVID-19.

OBJECTIVES	ENDPOINTS	JUSTIFICATION FOR ENDPOINTS
Primary		
To assess the safety of fostamatinib in hospitalized patients with COVID-19	Cumulative incidence of SAEs through day 29.	This endpoint was chosen to evaluate the safety of fostamatinib for the treatment of hospitalized patients with COVID-19.
Secondary		

*Abbreviated Title: Fostamatinib for COVID*

*Version Date: 09/17/2020*

OBJECTIVES	ENDPOINTS	JUSTIFICATION FOR ENDPOINTS

To assess the effect of fostamatinib on clinically relevant endpoints of disease course
	
 
1. Time to recovery by day 29: day of recovery is defined as the first day on which the subject satisfies one of the following three categories: Ordinal scale 3: hospitalized, not requiring supplemental oxygen-no longer requiring ongoing medical care; Ordinal scale 2: non-hospitalized, limitations on activities and/or requiring home oxygen; Ordinal scale 1: non-hospitalized, no limitations on activities
 
2. Number of days free of mechanical ventilation [patients with baseline ordinal scale 5-6 only]
 
3. Mortality at day 14 and 28
 
4. Grade 3 and 4 AE through day 60
 
5. Days of hospitalization
 
6. Ordinal scale at day 15 and day 29
 
7. Change in CRP, IL-6, ferritin, d-dimer, fibrinogen, absolute lymphocyte count, absolute neutrophil count, and platelet count from baseline [day 3, 5, 8, 11, 15, 29]
 
8. Number of days in the ICU [entire hospitalization]
 
9. Relative change in PaO2/FiO2 or SpO2/FiO2 ratio
 
10. Change in SOFA score from baseline (day 1) [day 3, 5, 8, 11, 15, 29]
 
11. Number of days on oxygen (Including nasal canula, HFNC, non-invasive, and mechanical ventilation)
 
12. Days free of renal failure [entire hospitalization]
 
	
Each of the secondary clinical endpoints were deemed to be clinically relevant indicates for improved or worsening disease course

*Abbreviated Title: Fostamatinib for COVID*

*Version Date: 09/17/2020*

OBJECTIVES	ENDPOINTS	JUSTIFICATION FOR ENDPOINTS
	
 
a. Renal failure defined as               
 
i. Increase in serum creatinine by <math>\geq 0.3</math>mg/dL within 48 hours or
 
ii. Increase in serum creatinine by <math>\geq 1.5</math> times baseline which is known or presumed to have occurred within the prior seven days, or
 
 
 
13. Clinically relevant deep vein thrombosis (DVT) or pulmonary embolism (PE) [entire hospitalization]
 
	
Tertiary/Exploratory		

1) To study the host immunological response to COVID-19 and potential mechanism of action of fostamatinib.
	
As an exploratory endpoint we will study the immune mechanism by which fostamatinib improves outcomes in patients with COVID-19.
 
 
1. Characterization of plasma biomarkers of immune activation
 
2. Measure platelet-leukocyte aggregates
 
3. Measure leukocyte activation assays
 
4. Measure plasma cytokine and chemokine levels
 
5. Evaluate the coagulation cascade
 
6. Measurement of immune antigen-antibody complexes
 
7. Measure thromboelastography (TEG)
 
8. Measure biomarkers of endothelial dysfunction
 
9. Characterize leukocyte extracellular traps
 
10. SARS-CoV-2 viability via cell culture from oropharyngeal samples
 
	
These exploratory endpoints are relevant ex vivo and in vitro analysis that will help determine disease and mechanisms of action while on fostamatinib

OBJECTIVES	ENDPOINTS	JUSTIFICATION FOR ENDPOINTS
	11. Detection of viral antigen blood and oropharyngeal samples	

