### **5.1 INCLUSION CRITERIA**

1. Patient must be hospitalized, or had their inpatient stay extended, for COVID-19.
2. Age  $\geq 18$  years
3. Subject (or legally authorized representative) provides informed consent prior to initiation of any study procedures.
4. Subject (or legally authorized representative) understands and agrees to comply with planned study procedures.
5. Females of childbearing potential must agree to be abstinent or use a medical acceptable form of contraception from the time of enrollment through 30 days after last day of study drug
6. Laboratory confirmed SARS-CoV-2 RT-PCR test within 7 days of enrollment
7. Illness of any duration with SpO2 of less than 94% on room air requiring supplemental oxygen via nasal canula or non-invasive mechanical ventilation, or mechanical ventilation or ECMO (5 to 7 on the 8-point scale)

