#### **9.3.3 Analysis of the Secondary Endpoint(s)**

To determine a subject's clinical status using the ordinal scale: On Day 1, report their clinical status at enrollment (start of study drug). On Day 2, report the period from enrollment to midnight on Day 1. On Day 3 through Day 11, or until discharged, and on Days 15, 22 and 29, provide the worst clinical assessment for the previous day (i.e., midnight to midnight; 00:00 –

23:59 (24-hr clock)). For example, on study Day 3 when completing the form, the worse clinical outcome measure of Day 2 is captured with the worst being death followed by ECMO, mechanical ventilation, etc. The Day 2 measurement is assessed as occurring anytime in that 24-hour period (00:00 to 23:59).

Secondary endpoints will be evaluated as follows:

1) The time to recovery by Day 29, it will be estimated by median and 95% confidence interval by study arm. The cumulative recovery rate will be estimated by the Kaplan-Meier method. The comparison between two treatment arms will be assessed by the log-rank test. The recovery ratio and hazard ratios will be based on the Cox model. The analysis will be stratified by disease severity at enrollment.

The time to recovery will be evaluate and censored up until Day 29. It is defined as the elapsed time in days from the day 1 to the earliest day at which a subject reaches recovery (having 1-3 of the 8-point ordinal scale). Any subjects that are lost to follow-up prior to an observed recovery will be censored at the day of their last observed assessment. Subjects who complete follow-up but do not experience recovery will be censored at Day 29. All deaths within Day 29 (and prior to recovery) will be considered censored at Day 29. Analysis will be based on intention to treat including all randomized patients. Patients who have received at least four doses of study drug will be considered in a sensitivity analysis for this secondary outcome.

2) Duration of events (e.g., mechanical ventilation or days in the ICU) will be summarized with median and interquartile rage by the study arms and compared between the treatment arms by Wilcoxon's rank sum test or log-rank test.

3) Binary events (e.g., need for intubation) will be summarized as percentages and 95% confidence intervals by the study arms and compared between the treatment arms by Fisher's exact test.

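### The window for ICU days, days free of renal failure and DVT/PE is not tied to Day 1, so read literally it takes in time and events from before randomisation

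*Combined protocol and SAP*

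**What the plan says.** Three secondary endpoints in section 3, repeated in the section 1.1 synopsis, share one bracketed window:

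- Endpoint 8: "Number of days in the ICU [entire hospitalization"]
- Endpoint 12: "Days free of renal failure [entire hospitalization"]
- Endpoint 13: "Clinically relevant deep vein thrombosis (DVT) or pulmonary embolism (PE) [entire hospitalization"]

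Endpoint 5, "Days of hospitalization", has no window at all, and neither does endpoint 11 (days on oxygen).

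Patients join after admission. Section 5.1, criterion 1 reads "Patient must be hospitalized, or had their inpatient stay extended, for COVID-19". Criterion 7 admits "Illness of any duration", including patients on mechanical ventilation or ECMO.

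Other endpoints have a stated origin. Section 9.3.3 defines time to recovery as "elapsed time in days from the day 1" to the first day of recovery, and section 3 takes SOFA change from Day 1. Section 4.1 defines Day 1 as the first day of study drug. For durations, section 9.3.3 names the Wilcoxon rank sum or log-rank test without giving an origin.

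**The concern.** A hospitalisation ordinarily begins at admission. On that meaning, a patient who spent six days in the ICU before enrolment brings six days into endpoint 8, and a PE diagnosed before the first dose is an event under endpoint 13. The drug cannot have influenced either.

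Such data add noise to the day counts, pull the clot comparison towards no effect, and let a chance difference in prior stay pass into the estimated treatment difference. Randomisation is stratified by site and severity (section 6.3.1), not by time since admission, so nothing in the design limits that difference directly. The documents also leave room for two analysts to produce different results from the same records. DVT/PE matters to the rationale, because reduced immunothrombosis is one of the hypothesised benefits (sections 2.2 and 2.3.3).

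**Working it through.** **What the text settles.** There is no planned figure to reproduce: section 9.1 bases the sample of about 60 (30 per arm) on feasibility and gives no rates, standard deviations or power. The first step is therefore to set the passages side by side.

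| Place | Bearing on the start of the window |
|---|---|
| 1.1 and 3, endpoints 8, 12, 13 | Whole hospital stay; no start day; nothing restricts DVT/PE to new events |
| 8.2.2, routine laboratory row | The same phrase, but with a Day 1 start attached |
| 8.2 | Clinical status recorded by study day to Day 60, and linked to the secondary outcomes |
| 1.3 | No column before Day -1 |
| 8.4.4 | Conditions present before the first dose are baseline and not reported as AEs |
| 9.3.3 | Origin given for time to recovery, none for durations |

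The laboratory row can be read either way: as a sign of what the phrase means throughout, or as a sign that the authors wrote Day 1 where they intended it. None of these places defines endpoints 8, 12 or 13.

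**What the literal reading would cost.** All rates, means and standard deviations below are assumptions. Only the 30 per arm comes from the plan. Tests are two-sided at 0.05.

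*ICU days, normal approximation.* Take a true difference of 5 days and a post-randomisation SD of 7. Prior days with SD s give a total SD of √(7² + s²), and power = Φ(5 / (SD × √(2/30)) − 1.96). With s = 0: 5 / (7 × 0.258) = 2.77, less 1.96 gives 0.81, so power is 79%. The 95% range for chance imbalance in mean prior days is ±1.96 × s × √(2/30).

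| SD of prior days | Total SD | Power | Chance imbalance (95%) |
|---|---|---|---|
| 0 | 7.00 | 79% | 0 |
| 2 | 7.28 | 76% | ±1.0 days |
| 4 | 8.06 | 67% | ±2.0 days |
| 7 | 9.90 | 50% | ±3.5 days |

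*ICU days, simulated Wilcoxon test.* Post-randomisation days are gamma with shape 1.5 and means 10 and 5.5; prior days are exponential; 10,000 replicates per setting. Counting from Day 1, power is about 70%.

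| Mean prior days | Power, all patients have prior ICU days | Power, half do |
|---|---|---|
| 1 | 68% | 68% |
| 2 | 65% | 65% |
| 4 | 55% | 58% |
| 6 | 45% | 51% |
| 8 | 38% | 46% |

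With equal arms and all patients given prior days, the rejection rate stays between 4.5% and 5.0%. With a prior mean of 6 days, the SE of the difference in prior means is 6 × √(2/30) = 1.55 days, so chance alone puts the arms more than 2 days apart in about 20% of trials.

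*DVT/PE.* If a fraction q already has a clot and p is the new-event rate, the counted rate is q + (1 − q)p. For 15% vs 7.5%:

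- q = 10%: 0.10 + 0.90 × 0.15 = 23.5%, and 0.10 + 0.90 × 0.075 = 16.75%. The risk ratio is 0.71 instead of 0.50.
- q = 5%: 19.25% vs 12.1%, a risk ratio of 0.63.

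Exact Fisher power at these rates is about 5% with or without prior clots (5.3% at q = 0, 5.2% at q = 10%), so here the dilution moves the estimate and not the test. With a larger assumed effect, 30% vs 10%, power is 37% at q = 0 and 30%, 25% and 17% at q = 5%, 10% and 20%; the 20-point difference becomes 19, 18 and 16 points. With 20% in both arms, the Fisher rejection rate stays at 2.2% to 2.6% for q from 0 to 20%.

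**The case against.** The strongest reply is that the trial would in practice count from Day 1. Status is captured by study day, the schedule starts at Day -1, pre-dose conditions are baseline for AE purposes, and the laboratory table gives the same phrase a Day 1 start. That evidence is real, and it rules out stating as fact that the window begins at admission. But these are collection schedules and an AE reporting rule. Prior ICU dates and clots are in the medical record, which section 8.1.1 allows to be reviewed at screening, so nothing stops them being counted. The ambiguity stands.

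Second, entry is not wholly open. Criterion 6 requires a positive RT-PCR within 7 days of enrolment, and section 5.2 excludes eGFR below 30 ml/min, shock or hypotension, and suspected sepsis. These make long prior ICU stays and severe prior renal failure less likely. They do not cap prior stay, since a repeat test can meet criterion 6. Nor do they exclude an existing clot or renal failure as section 3 defines it, by a rise in creatinine.

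Third, the larger power losses assume that everyone has prior ICU days, whereas patients on nasal cannula are eligible. This stands: with a prior mean of 1 or 2 days the loss is only about 2 to 5 points.

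A reader might infer that counting prior time biases the comparison or manufactures a drug effect. The documents do not support that. Allocation is randomised 1:1, prior time is balanced in expectation, and the null rejection rates above do not rise.

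**Conclusion.** The point holds in a limited form. Endpoints 8, 12 and 13 have a window whose start is undefined and whose literal meaning includes time before randomisation. Whether such data would actually have been counted cannot be determined from the documents. Endpoints 5 and 11 do not carry the bracket; their fault is that they state no window.

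The consequence is added variance, attenuation and exposure to chance imbalance in prior stay. In the ICU-day scenarios, power falls by 2 to 32 percentage points for mean prior stays of 1 to 8 days. For clots, a true risk ratio of 0.50 is read as 0.63 to 0.71 with 5% to 10% prior clots. These figures rest on assumed inputs and show scale only.

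The primary endpoint, SAEs through day 29, has its own window and is untouched. Confidence is moderate, and the change is a cheap improvement to secondary endpoints. How the window ends (discharge, death, readmission, Day 60) is a separate question.

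**What to change.** In sections 1.1 and 3:

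- State that endpoints 8, 12 and 13 count from Day 1, the day of the first dose.
- State that only DVT/PE first diagnosed after the first dose counts for endpoint 13.
- Report clots, renal failure and ICU days before Day 1 as baseline characteristics by arm.
- Give endpoints 5 and 11 the same Day 1 origin.
- For endpoint 12, say which creatinine value is the baseline in the 1.5-fold criterion, so that renal status at Day 1 is well defined.

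Repeat the origin in section 9.3.3, item 2, beside the tests for durations.

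The change needs no extra patients or visits. Clot, renal and ICU status at Day 1 must be abstracted from the record; no CRF is among the documents, so whether it already has fields for this is unknown. The small downside is that fewer DVT/PE events and ICU days will be counted, but those dropped could not have responded to the drug.
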